1.6 Study Variables

A. Independent Variables, Interventions, or Predictor Variables

This is a randomized by sex, double-blind, placebo controlled trial. A placebo is needed to minimize potential behavioral changes with pharmacological intervention. This will isolate the effects of exercise intensity based training on respective outcomes. As a result, exercise at low or high intensity with placebo will serve as standard of care/control, while exercise at low or high intensity with metformin will be the experimental conditions. Pre and post test data will be compared statistically.

Data will be analyzed using R (Vienna, Austria, 2011). A two-way repeated measures analysis of variance (ANOVA) will be used to assess time course differences (group x test). Bonferonni post-hoc analysis will be used to determine group differences and paired t-tests will be used to assess within treatment effects. Linear regression analyses will be used to identify relationships between respective variables. A *P*<0.05 will be considered statistically significant. Data will be expressed as mean ± SEM.

12/31/2499

The same statistical approach for secondary analysis will be conducted as the primary variable analysis.

B. Dependent Variables or Outcome Measures

- 1. Insulin Sensitivity
- 2. Fitness (e.g. VO2max, physical activity amount, heart rate, RPE, etc.)
- 3. Body composition (e.g. weight, fat, FFM, BMD, waist circumference, etc.)
- 4. Vascular Function (e.g. FMD, CEU, heart, arterial stiffness, etc.)
- 5. Questionnaires (e.g. Sleep, activity, quality of life, hunger, etc.)
- 6. Glucose (e.g. substrate, isotope)
- 7. Lipid Profile (e.g. TG. HDL. FFA. etc.)
- 8. Blood clinical chemistries (e.g. CBC)
- 9. C-peptide
- 10. Insulin
- 11. Inflammation (e.g. endothelin-1, adiponectin, Microparticles, etc.)
- 12. Nitrates
- 13. Gut hormones (e.g. ghrelin, GLP-1, etc.)
- 14. Pregnancy (in females), blood for screening at each admission.
- 15. Energy metabolism (e.g. rest, exercise, insulin-stimulation).
- 16. Gut microbiota
- 17. Cognitive measures using NIH toolbox

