1.5 Sample Size Justification

The primary outcome for this study will be changes of basal flow mediated dilation (FMD) before the insulin clamp pre and post intervention. Based on our prior work 47, with 15 subjects per treatment arm we expect to have at least an 80% chance of rejecting the null hypothesis that the mean pre to post-exercise change in FMD is the same for any pair of treatments if the true means of the underlying distributions differ by more than 4.2%. Details: In computing the minimum detectable effect size of 4.2%, we assumed that the measurements for pre to post-treatment change in FMD will be normally distributed and that the measurement variability in the pre to postexercise FMD changes is the same regardless of the treatment. Moreover, we assumed that the standard deviation of the underlying distributions is 3.4% based on our prior work 47, which is notably larger than reported in the metformin literature 48. To account for a total of 6 pairwise between-treatment comparisons, a Bonferroni corrected experiment-wise type I error of 0.05 was utilized to derive the minimum detectable between-treatment difference of 4.2%. Limitations: We do not have data from the literature or from our own studies with exercise to estimate power on changes in MBV, nor with the combination of exercise+metformin. However, considering MBV, we based our estimate of sample size on our study examining the effect of insulin on MBV in both skeletal and cardiac muscle in the control setting and in the setting of elevated plasma FFA. We observed that insulin significantly increased microvascular blood volume (MBV) at both sites (p<0.01) in the absence of elevated FFA and this effect was entirely blocked by elevating plasma FFA. These observations were made in 22 subjects, although less would have yielded significance ^{36, 42}. Moreover, previous work that we conducted with HiEx+metformin demonstrated significant blunting effects on systolic blood pressure vs. exercise alone with only 8 people per group 5. Anticipated dropout: Based on our prior work with this study population, we anticipate that the study participant dropout rate will be 10-15%. Therefore, we intend to enroll 80 subjects with 20 subjects randomized to each treatment intervention.

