4.3 Number of Subjects

A. Total Number of Subjects

12/31/2499

Based on prior work by our group, we anticipate that approximately 25% of subjects who enroll in the study will withdraw/drop out early. Currently the study requires 45 people of 80 given it is a transfer project when our team was at the University of Virginia. In addition, we expect that 70% of individuals who we screen/consent will not qualify. **Thus, we expect to screen 225 subjects of whom about 67 will participate and 45 will complete the study.**

B. Total Number of Subjects If Multicenter Study

NA

C. Feasibility

We are confident that we can recruit the required number of health volunteers given the population in and surrounding Rutgers University. We are also confident we can recruit patients with risk factors for metabolic syndrome in the Clinical Academic Building at RWJMS.

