6.0 Data Management Plan

6.1 Data Analysis

Describe the data analysis plan. Include any statistical procedures and power analysis, if applicable to the research.

12/31/2499

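### The primary FMD comparison uses raw change scores, without baseline FMD or sex in the model: valid, but it gives up precision that adjustment would recover at no data cost

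*Combined protocol and SAP*

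**What the plan says.** Section 1.5 defines the endpoint as a change score: "The primary outcome for this study will be changes of basal flow mediated dilation (FMD) before the insulin clamp pre and post intervention". Section 1.6 A gives the only model for comparing arms: "A two-way repeated measures analysis of variance (ANOVA) will be used to assess time course differences (group x test"). It continues: "Bonferonni post-hoc analysis will be used to determine group differences and paired t-tests will be used to assess within treatment effects". Linear regression is mentioned there only for relationships between variables. No covariate is named for the treatment comparison.

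The same section states: "This is a randomized by sex, double-blind, placebo controlled trial". It also carries the approach over to the other endpoints: "The same statistical approach for secondary analysis will be conducted as the primary variable analysis".

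Section 6.1, where further model terms might be expected, holds only the template instruction: "Describe the data analysis plan. Include any statistical procedures and power analysis, if applicable to the research".

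Both candidate covariates are already available. Basal FMD is measured at the start of the clamp before and after the intervention (section 1.3 A and the schedule in section 1.10), and sex is known at randomisation.

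**The concern.** A change score fixes the coefficient of baseline FMD at 1. ANCOVA estimates that coefficient from the data. With equal pre and post variances the estimated slope is below 1 whenever the correlation is below 1, so the change-score comparison then carries avoidable residual variance.

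Sex is a separate matter. If randomisation balances sex across arms and sex predicts FMD change, leaving it out keeps between-sex variation in the error term. The test becomes conservative.

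Neither omission biases the comparison. What is at stake is the width of the intervals and the power of six pairwise contrasts, each tested at 0.05/6 with a planned 15 subjects per arm. The same loss carries over to any secondary endpoint with a baseline value.

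**Working it through.** **Inputs from section 1.5.** SD of change 3.4 ("we assumed that the standard deviation of the underlying distributions is 3.4% based on our prior work 47"); 15 per arm in four arms; target difference 4.2; six comparisons, so alpha = 0.05/6 = 0.00833 each; power of at least 80%.

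**Assumed.** Two-sided tests (not stated). Pre-post correlation of FMD, rho, from 0.3 to 0.8 (not given). Equal pre and post variances unless stated otherwise.

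**1. The plan's own figure.** Standard error of a pairwise difference = 3.4 × √(2/15) = 1.2415.
- Normal approximation: detectable difference = (2.638 + 0.842) × 1.2415 = 4.32. Power for 4.2 is 77.2%, and 16 per arm are needed. The stated 15 per arm is within one subject, but the stated 80% is not reached.
- Noncentral t with pooled error (56 df): critical t 2.735, noncentrality 4.2/1.2415 = 3.383. Power is 73.9%, detectable difference 4.46, and 17 per arm are needed for 80%.

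**2. What the planned test is.** With two time points, the group x test F and the one-way ANOVA F on change scores are the same statistic. In a test data set both were 0.1157.

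**3. ANCOVA with equal variances.** Let σ be the common pre and post SD. Var(change) = 2σ²(1 − rho), and the ANCOVA residual variance is σ²(1 − rho²). Their ratio is (1 + rho)/2, so the residual SD is 3.4 × √((1 + rho)/2). With baseline and sex in the model, and sex explaining nothing, there are 54 df and the critical t is 2.739.

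| rho | variance ratio | residual SD | power for 4.2 | detectable difference | n per arm for 80% |
|---|---|---|---|---|---|
| planned test | 1 | 3.40 | 73.9% | 4.46 | 17 |
| 0.3 | 0.65 | 2.74 | 92.2% | 3.60 | 12 |
| 0.5 | 0.75 | 2.94 | 87.3% | 3.87 | 13 |
| 0.7 | 0.85 | 3.13 | 81.9% | 4.12 | 15 |
| 0.8 | 0.90 | 3.23 | 79.2% | 4.24 | 16 |

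Chance baseline imbalance inflates the contrast variance by about 1.02. That lowers the ANCOVA powers to about 91.6%, 86.4%, 81.0% and 78.1%. Simulation of 20,000 trials per rho agrees: 73.5–74.2% for the planned test, and 91.8%, 86.6%, 80.6% and 78.4% for ANCOVA.

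**4. Unequal variances.** With k = post SD/pre SD, the ratio is k²(1 − rho²)/(1 + k² − 2·rho·k). At k = 1.25 it is 0.784, 0.893 and 1.000 for rho 0.3, 0.5 and 0.8, giving detectable differences of 3.95, 4.22 and 4.46. In the last case there is no gain, and chance imbalance leaves ANCOVA about one point worse (72.6% against 73.9%).

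**5. Sex.** At rho 0.5, if sex explains 0, 5 or 10% of the residual variance, ANCOVA power is 87.3%, 89.2% or 91.1%. In simulations with sex balanced across arms (16 per arm), the unadjusted contrast at nominal 0.05 rejected in 0.050, 0.044 and 0.038 of null trials when sex explained 0, 5 and 10% of the variance of change.

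**The case against.** The endpoint, the power calculation and the analysis all concern change in FMD, so the plan is consistent with itself and the test is valid. That stands, and it makes this an improvement rather than the correction of an error.

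The gap between 73.9% and the stated 80% comes from the sample-size inputs, not from a missing covariate. That also stands. Adjustment could close the gap but did not cause it.

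Section 1.5 enrols 20 per arm and expects 10–15% dropout, which leaves 20 × 0.85 = 17 to 20 × 0.90 = 18 completers. The planned test then has 80.6% to 83.5% power. However, section 4.3 expects about 25% dropout, which leaves 20 × 0.75 = 15. Even at 17 per arm, ANCOVA at rho 0.5 with equal variances has 92.0% against 80.6%.

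The size of the gain rests on a correlation and a variance ratio that the documents do not give. This is a real limit. If the post SD is 1.1 times the pre SD, power at rho 0.7 is about 77.0% after allowing for chance imbalance. At 1.25 times and rho 0.5 it is about 78.6%. Both exceed 73.9% but miss 80%.

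The case for sex is weaker than the case for baseline FMD. The documents describe no strata or blocks, and nothing in them shows that sex predicts FMD change. The argument left is that the term matches the stated randomisation and costs one degree of freedom.

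**Conclusion.** The concern holds as a loss of efficiency, not a bias. It is worth changing, but the planned between-arm comparison is not invalid.

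Under equal variances, baseline adjustment cuts the error variance by (1 − rho)/2: 35% at rho 0.3, 25% at 0.5, 15% at 0.7 and 10% at 0.8. At 15 per arm it reaches the stated 80% if rho is about 0.7 or lower. If variance rises after the intervention, the gain shrinks. In the least favourable case examined, the cost is about one point of power, against a gain of about 18 points in the most favourable (92.2% against 73.9%). Adding sex gains nothing if sex does not predict FMD change.

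The conclusion assumes two-sided tests, pooled error and a model with only the pre and post values.

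**What to change.** In section 1.6, and in section 6.1 when it is completed, pre-specify before unblinding:

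- **Primary analysis:** ANCOVA of post-intervention basal FMD (or its change) on arm (four levels), baseline basal FMD and sex. Take the six Bonferroni-adjusted pairwise contrasts from this model.
- **Sensitivity analysis:** the group x test ANOVA as now written.
- **Time points:** state that the primary model uses the pre- and post-intervention clamp visits, since FMD is also measured at Visit 58.
- **Secondary endpoints:** use the same form of model, with each endpoint's own baseline value.
- **Transferred data:** section 4.3 says "Currently the study requires 45 people of 80 given it is a transfer project when our team was at the University of Virginia". State whether data from the earlier institution are pooled. If they are, add an institution term.

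The cost is wording only. Both covariates are already collected. At 15 per arm, error df fall from 56 to 54 and the critical t rises from 2.735 to 2.739, about 0.14%. An institution term would cost one more degree of freedom.

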1.0 Research Design

1.1 Purpose/Specific Aims

The overall purpose of the study is to test the effect of metformin on exercise intensity based training adaptations in adults with metabolic syndrome.

A. Objectives

Understand effect of metformin on training intensity mediated vascular versus metabolic insulin sensitivity in adults with metabolic syndrome for clinical health.

B. Hypotheses / Research Question(s)

The overarching hypothesis is that metformin may blunt adaptation following high intensity exercise by lowering/attenuating oxidative stress. Thus, compared with high intensity exercise plus metformin, low intensity exercise plus metformin will produce greater vascular insulin sensitivity and metabolic insulin sensitivity changes following 16 weeks of treatment. In addition, we anticipate that high intensity exercise based training alone will produce greater effects than low intensity exercise. Lastly, we hypothesize that these changes in metabolic and vascular insulin sensitivity will correlate with glycemic control and blood pressure changes.

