1.2 Research Significance

Metabolic Syndrome (MetS) is associated with a 3-fold cardiovascular disease (CVD) mortality risk compared with healthy controls, and it is estimated that 40% of the U.S. will have MetS by 2020 (1). MetS is characterized by elevated blood glucose, hypertension, carotid artery thickness, dyslipidemia, and obesity (2). Although skeletal muscle insulin resistance is an important underlying cause of MetS, vascular insulin resistance, particularly at the microvasculature level, may actually contribute to the pathogenesis of metabolic insulin resistance and drive the CV complications in type 2 diabetes (T2D) (3). Here we propose that vascular insulin resistance is central to CVD risk reduction in MetS and interventions are needed that target enhancing endothelial function and decreasing arterial stiffness. High intensity exercise (HiEx) is an established treatment to reduce CVD risk in MetS patients (4-7) by, in part, improving basal endothelial function and arterial stiffness (8-10), although this has not tested under insulin-stimulated conditions. Metformin is a 1st line agent to treat hyperglycemia due to in part to its ability to reduce hepatic glucose output, and protect against CV morbidity and mortality as evidenced by the UKPDS (11). Surprisingly, our preliminary work in MetS/prediabetic individuals shows that metformin may ameliorate CVD risk, but when combined with HiEx there tends to be a blunting effect on skeletal muscle metabolic insulin resistance (12). One attractive alternative to promote vascular and metabolic adaptation, and test the additive effects of metformin on exercise, is to prescribe exercise that does not primarily rely on mitochondrial oxidative stress to induce adaptation, i.e. low intensity exercise. Herein, we propose that metformin may interact with exercise in an intensity based manner for adaptations related to skeletal muscle metabolic and/or vascular insulin resistance. These findings will have direct impact on public health for glycemic control and blood pressure regulation as well as inform how metformin interacts with physical activity behavior.

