 - Subjects will be required to wear clothes without metal on them (including zippers and bras with an underwire). If clothes have metal, we will ask that subjects change into a pair of shorts and a t-shirt or wear a lab hospital gown.
 - If there are technical issues with the DEXA machine we will measure the total amount of fat and muscle in the subjects body with the BodPod® in the IFNH.
 - We will provide a swimsuit and swim cap for subjects to wear during this procedure to help standardize the results. The swimsuit and swim cap are provided to get accurate results. Subjects will not get wet at any time during this test. Subjects will enter the device and sit down. A door will close while the subject sits in the BodPod®. They are asked to breath normal and be still. The BodPod® looks like a large white egg with a window on the door.

NOTE: in the event of scheduling conflicts, cardiovascular fitness and/or body composition assessments may be completed within 1 week of doing the OGTT during Visit 58.

END OF STUDY:

After subjects have completed Phase 5, the study will be complete.

B. Data Points

We are collecting blood and urine during experimental visits. Vital signs, including blood pressure, temperature, heart rate, as well as aerobic fitness, body composition, resting metabolism, non-exercise physical activity, appetite, as well as quality of life. Please see the study overview (Study Duration) that outlines when outcomes will be collected.

C. Study Duration

Subjects participation in this study will require about **58** study visits over about 7-8 months. Each visit will last between **1-6** hours depending on whether it is for research purposes (e.g. about 3-6 hours) or exercise training (e.g. 1-1.5 hours). There are 2 Screening Visits and 5 Test Visits. Thus, the majority of visits include exercise training (48 visits).

D. Endpoints

The primary outcome for this study will be changes of basal FMD before the insulin clamp pre and post intervention. We will also examine the influence of insulin on FMD as well as metabolic insulin sensitivity, defined as the glucose infusion during the last approximate 30 minutes of the clamp procedure. Together, these findings will help tease out vasculature vs. metabolic insulin sensitivity differences between treatments. Correlations will be conducted to understand the relationship between endothelial function and metabolic insulin sensitivity with substrate oxidation,

12/31/2499

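### The 2x2 trial proposes that metformin's effect depends on exercise intensity, but no planned analysis estimates the metformin x intensity contrast

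*Combined protocol and SAP*

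**What the plan says.** Section 1.3 (Phase 3) lists four arms: low or high intensity exercise, each with placebo or metformin. This is a 2x2 layout.

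Section 1.2 proposes that "metformin may interact with exercise in an intensity based manner for adaptations related to skeletal muscle metabolic and/or vascular insulin resistance". Section 1.1 B states two directional hypotheses. Compared with high intensity plus metformin, "low intensity exercise plus metformin will produce greater vascular insulin sensitivity and metabolic insulin sensitivity changes following 16 weeks of treatment". Without the drug, "we anticipate that high intensity exercise based training alone will produce greater effects than low intensity exercise". Taken together, they say that the intensity effect changes sign with metformin.

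The analysis is set out in Section 1.6 A: "A two-way repeated measures analysis of variance (ANOVA) will be used to assess time course differences (group x test"). Then "Bonferonni post-hoc analysis will be used to determine group differences and paired t-tests will be used to assess within treatment effects". Secondary outcomes are handled in the same way, and results are shown as mean ± SEM. Section 6.1 holds only the template prompt.

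Section 1.5 sizes the trial on basal FMD, with the null hypothesis that the mean "change in FMD is the same for any pair of treatments". The alpha is split "To account for a total of 6 pairwise between-treatment comparisons". Section 1.3 D makes basal FMD the primary outcome and adds the insulin-related ones: "We will also examine the influence of insulin on FMD as well as metabolic insulin sensitivity".

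Nowhere in the text available for review is group split into drug and intensity, and no drug x intensity term, difference in differences, or interval for one is named.

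**The concern.** The two factors of the planned ANOVA are group (four levels) and test (pre, post). The group x test term therefore asks whether the four mean changes differ in any way. Its three degrees of freedom pool the drug effect, the intensity effect and their interaction, and only the last bears on the proposal in Section 1.2.

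The pairwise tests come closer but still do not give the missing quantity. Each pair estimates one simple effect. None estimates the difference between two simple effects, which is what a statement that metformin's effect depends on intensity requires. The plan does contain one valid route to such a statement: both intensity pairs significant in opposite directions. That route is demanding, and it yields no interval for the size of the interaction.

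At stake is whether the trial can say, with a stated margin of error, how far metformin's effect differs between low and high intensity training.

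**Working it through.** **Inputs.** From Section 1.5: SD of change 3.4 points, equal in all arms; 15 evaluable per arm; 4.2-point pairwise difference; 80% power; experiment-wise alpha 0.05 over six pairs, so 0.05/6 = 0.00833 per pair; 20 randomised per arm; 10-15% dropout. Assumptions: two-sided tests (sidedness is not stated), a pooled residual SD with 4n − 4 df, and the effect patterns below.

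**The plan's own figure.** By the normal approximation, n per arm = 2 × [(2.638 + 0.842) × 3.4 / 4.2]² = 15.9, so 16 against the stated 15. The inputs are therefore those behind the plan's sample size. The small gap is a separate sample-size question and is not used here.

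**The contrast.** On pre-to-post change,

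C = (HiEx+Met − LoEx+Met) − (HiEx+Plac − LoEx+Plac).

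This also equals metformin's effect at high intensity minus its effect at low intensity. Its standard error is SD × √(4/n) = 3.4 × √(4/15) = 1.76. With 56 df, the 95% half-width is 2.003 × 1.756 = 3.52. Power and minimum detectable effect (MDE, 80% power, alpha 0.05) come from the noncentral t:

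| Evaluable per arm | SE | 95% half-width | MDE | Power for 4.2 |
|---|---|---|---|---|
| 15 | 1.76 | 3.5 | 5.0 | 65% |
| 17 (15% dropout of 20) | 1.65 | 3.3 | 4.7 | 71% |
| 18 (10% dropout of 20) | 1.60 | 3.2 | 4.6 | 73% |
| 20 (no dropout) | 1.52 | 3.0 | 4.3 | 78% |

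At 21 per arm power is 79.9%, and at 22 it is 81.7%. So 80% power for 4.2 points needs about 22 completers per arm, more than the 20 randomised.

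**The route the plan already contains.** A pair has SE 3.4 × √(2/15) = 1.242. At 0.05/6 with 56 df the critical value is 2.735, so each observed difference must exceed about 2.735 × 1.242 = 3.40 points. Significance of both pairs in opposite directions thus needs an observed contrast of at least 2 × 3.40 = 6.8 points. The contrast alone needs 2.003 × 1.756 = 3.5 at alpha 0.05, or 2.735 × 1.756 = 4.8 at 0.05/6.

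Assumed pattern: HiEx is better than LoEx by d on placebo and worse by d on metformin, so the true interaction is 2d in size. At 15 per arm (pairs by simulation, 1,000,000 trials per setting):

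| d | Interaction (2d) | Both pairs significant, opposite directions | Contrast, alpha 0.05 | Contrast, alpha 0.05/6 |
|---|---|---|---|---|
| 2.1 | 4.2 | 3% | 65% | 37% |
| 3 | 6.0 | 16% | 92% | 75% |
| 4.2 | 8.4 | 55% | 99.7% | 98% |

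**Where the planned pair does better.** Suppose metformin removes 4.2 points at high intensity and does nothing at low intensity. The contrast is then 4.2 points, with 65% power at alpha 0.05. The HiEx+Metformin versus HiEx+Placebo pair has 74% even at 0.05/6, because its SE is smaller.

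**The case against.** The strongest reply is that the formal hypotheses in Section 1.1 are simple effects, and the planned pairs test them. Low against high intensity on metformin is one of the six pairs, and high against low on placebo is another. Blunting within high intensity, the prior signal cited in Sections 1.2 and 1.4, is a third. The interaction wording comes from the significance section. All this stands. A reader might infer that the plan leaves its stated hypotheses untested, but the documents do not support that.

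A reader might also infer that the omnibus term will be reported as an interaction test, or that a significant pair will be set against a non-significant one. Section 1.6 says neither. It uses the omnibus for differences over time and states no rule for comparing pairs, so neither misuse is counted as a harm here.

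The power comparison is uneven. It sets two tests at 0.05/6, both required, against one test. The symmetric crossover is also the contrast's best case, because all the signal lies in the interaction. At matched alpha the advantage shrinks but remains (37%, 75% and 98% against 3%, 16% and 55%). The two routes also support different claims: a significant contrast shows that the intensity effect differs by drug, while a claim of reversal still needs both pairs.

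Finally, Sections 1.1 and 1.2 speak of vascular and metabolic insulin sensitivity or resistance, whereas every figure here is for basal FMD, measured before insulin. The documents give no SD for the insulin outcomes, so nothing is quantified for them.

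None of this supplies the estimate. The pairs do not give the difference between simple effects, and no interval for it is planned.

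**Conclusion.** The point holds as a missing estimate. The planned tests are valid for the hypotheses in Section 1.1, and two significant intensity pairs in opposite directions would properly show a crossover. But the plan provides no estimate, test or confidence interval of the metformin x intensity contrast for any outcome, although the design can supply one and Section 1.2 proposes the interaction.

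For basal FMD, the only valid route in the plan would miss most symmetric crossovers of 2.1 or 3 points per intensity pair and nearly half of those of 4.2 points. The contrast would detect a differing intensity effect more often at either alpha. This rests on the protocol's SD of 3.4%, 15 completers per arm, equal variances, two-sided tests and an assumed pattern that favours the contrast. It does not show that the contrast is better for every pattern: blunting confined to high intensity is better tested by its own pair. Nor is the contrast well powered at this size. The matter is a worthwhile, inexpensive improvement rather than a flaw that invalidates the planned analysis.

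**What to change.** In Section 1.6 A:

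- Code drug and intensity as two factors. Prespecify the 1-df metformin x intensity contrast on pre-to-post change, with its 95% CI, as one secondary estimate for basal FMD. Give the same contrast as a supportive estimate for insulin-stimulated FMD and clamp insulin sensitivity.
- Base any statement that metformin's effect depends on intensity on that contrast, not on one pair being significant and another not. Reserve a claim of reversal for both intensity pairs being significant in opposite directions.
- Keep the group x test omnibus and all six Bonferroni pairs. The contrast neither gates them nor is gated by them.
- State the precision for basal FMD at 15 per arm: SE 1.76, half-width 3.5 points, MDE 5.0 points, 65% power for a 4.2-point interaction (71% at 17 per arm, 78% at 20). Say in advance that a non-significant contrast is not evidence of no interaction. The sponsor must supply an SD before precision can be stated for the insulin outcomes.

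The cost is a few sentences and one extra contrast per outcome from data already planned. There are two downsides. Power is limited, so the interval will often be inconclusive. And a contrast tested at 0.05 outside the pairwise family raises the error bound for basal FMD to about 0.05 + 0.05 = 10%, with further additions for the supportive outcomes. For both reasons the report should emphasise the interval rather than the p-value.
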